#### 7.2 OTHER EFFICACY PARAMETERS DEFINED IN THE IWCLL GUIDELINES

The following parameters will be assessed according to the IWCLL guidelines (Hallek, Cheson et al. 2008) by repeated tumor assessments by clinical examination performed within 3 weeks before the first dosing, at week 4, week 8, afterwards at all visits until EOS and CT scans planned at baseline, week 4, week 16, and whenever a progression or a CR are suspected.

# 7.2.1 Partial response (with the addition of PR with lymphocytosis)

#### PR is defined as:

- A decrease in the number of blood lymphocytes by 50% or more from the values before start of IPH2201 treatment
- Reduction in lymphadenopathy (by CT scans in clinical trials or by palpation in general practice) as defined by:
  - A decrease in lymph node size by 50% or more either in the sum products of up to 6 lymph nodes or in the largest diameter of the enlarged lymph node detected prior to treatment

#### CONFIDENTIAL

Release date: Edition number

MOD-3783

12 August 2016

**GED** version

- No increase in any lymph node, and no new enlarged lymph node. In small lymph nodes (< 2cm), an increase of less than 25% is not considered to be significant

- A reduction in the noted pretreatment enlargement of the spleen or liver by 50% or more, as detected by CT scan or palpation
- The blood count should show one of the following results:
  - Neutrophils more than 1.5x10^9/L (1,500 μL) without need for exogenous growth factors
  - Platelets count greater than 100 x109/L (100,000/µL) or 50% improvement over baseline without need for exogenous growth factors
  - Hemoglobin greater than 110 g/L (11.0 g/dL) or 50% improvement over baseline without requiring red blood cell transfusions or exogenous erythropoietin

# 7.2.2 Progressive disease

Progressive disease during or after treatment is characterized by at least one of the following:

- o Lymphadenopathy. Progression of lymphadenopathy is often discovered by physical examination and should be recorded. In CLL, the use of CT scans usually does not add much information for the detection of progression or relapse. Therefore, the use of imaging methods to follow CLL progression is at the discretion of the investigator. Disease progression occurs if one of the following events is observed:
  - Appearance of any new lesion, such as enlarged lymph nodes (>1.5 cm), splenomegaly, or other organ infiltrates
  - An increase by 50% or more in greatest determined diameter of any previous site.
- An increase in the previously noted enlargement of the liver or spleen by 50% or more or the de novo appearance of hepatomegaly or splenomegaly
- An increase in the number of blood lymphocytes by 50% or more with at least 5000 B lymphocytes per microliter
- Transformation to a more aggressive histology (e.g., Richter syndrome). Whenever possible, this diagnosis should be established by lymph node biopsy
- Occurrence of cytopenia (neutropenia, anemia, or thrombocytopenia) attributable to CLL
  - During treatment. Cytopenias may occur as a side effect of many therapies and should be assessed according to the Grading scale for hematologic toxicity in CLL studies (see appendix IV). During treatment, cytopenias cannot be used to define disease progression
  - After treatment. The progression of any cytopenia (unrelated to autoimmune cytopenia), as documented by a decrease of hemoglobin levels by more than 20 g/L (2 g/dL) or to less than 100 g/L (10 g/dL), or by a decrease of platelet counts by more than 50% or to less than 100 x10^9/L (100,000/µL), which occurs at least 3 months after treatment, defines disease progression, if the marrow biopsy demonstrates an infiltrate of clonal CLL cells

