- Tumor Assessment: pretreatment tumor assessment should be performed within 3 weeks before the first dose. Tumor assessments by physical examination should be performed at W4, W8; afterwards at all visits until EOS. A CT scan (with contrast unless contraindicated) of the chest, abdomen, and pelvis is required for the pretreatment tumor assessment. New CT-scan should be performed at W4 visit, at W16 visit, at EOS, and to confirm any CR or progression-
- Follow up visits, after EOT and during 12 months: follow-up visits FU1 to FU4 to be performed monthly and hereafter follow-up visits FU5 2 months after FU4, FU6 and FU7 to be performed every 3 months.
- For patients in phase 1b part, PK assessments at W0 H0 (pre-dose), H0+1 (end of IPH2201 infusion) and H0+3 (2 hours after end of IPH2201 infusion); W0D2 (24 hours after end of IPH2201 infusion, +/- 6 hours); W0D8 W2 at H0 (pre-dose), H0+1 and H0+3; W4 at H0 (pre-dose), H0+1 and H0+3; W4D2; W4D8; W6, W12, W20, W28, W36, W14 and W52 visits, at H0 and H0+1; at EOT, FU1 to FU7 and EOS
- 18
  19 Include detection of genetic abnormalities usually associated to CLL, IgVh mutational status and ZAP 70 methylation profile

Include detection of genetic abnormalities usually associated to CLL, IgVh mutational status and ZAP 70 methylation profile

20

A bone marrow examination is required at screening visit if not performed within 1 month; at C3D1 it is optional and requires a specific consent from the patient; at least 2 months after the achievement of complete response (CR) criteria clinically and in peripheral blood, in order to confirm the CR; and in the event of disease progression.

Release date: 12 August 2016
Edition number

GED version MOD-3783

PHASE II Flow-chart	Screening 	W0 C1	W0D2  C1	W2 C2	W2D2 C2	W4 C3	W6 C4	W8 to W48 C5 to C15	EOT  W52	FU1 to FU4 	EOS 
Informed consent	Х									1	
Inclusion / Exclusion criteria	Х	X									
Demography, Medical history	Х										
Concomitant illness,	Х	X	X	X	X	X	X	Х	X	X	X
Concomitant medication	Х	X	X	X	X	X	X	X	X	X	X
Tumor assessment 	Х					Х		Х	X	X	X
IPH2201 administration 		Х		X		Х	Х	Х			
Ibrutinib administration 		Х	X	X	Х	X	Х	Х	X	X	
Safety assessments											
Weight	Х	Х		Х		Х	Х	X	Х	Х	Х
Height	Х										
Physical examination⁴	Х	X		Х		X	Х	X	X	Х	Х
Vital signs	X	X	Х	X	X	X	Х	X	X	X	X
ECOG status	Х	Х		Х		X	Х	X	X	Х	Х
Adverse events		Х	X	Х	Х	Х	Х	X	X	Х	X

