- 14 Tumor Assessment: pretreatment tumor assessment should be performed within 3 weeks before the first dose. Tumor assessments by physical examination should be performed at W4, W8; afterwards at all visits until EOS. A CT scan (with contrast unless contraindicated) of the chest, abdomen, and pelvis is required for the pretreatment tumor assessment. New CT-scan should be performed at W4, and thereafter at W16 and at EOS, and to confirm any CR or progression.
- 15 Follow up visits: to be performed every 3 months after EOT and during 12 months
- 16
  17 For patients in Phase 2a part, PK assessments at W0 H0 (pre-dose) and H0+1 (end of IPH2201 infusion); W0D1, W6, W12, W20, W28, W36, W44, W52 at H0 and H0+1; EOT, FU1 to FU4 (every 3 months); EOS

A bone marrow examination is required at screening if not performed within 1 month; at least 2 months after the achievement of complete response (CR) criteria clinically and in peripheral blood, in order to confirm the CR; and in the event of disease progression.

Release date: Edition number

MOD-3783

12 August 2016

GED version

Correlation tables of visit names between Protocol V4.0 and Protocol V5.0 for patients enrolled according to previous versions of protocol

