### Week 6 day 2 (W6D2)

To be performed 24 hours +/- 6 hours after the administration visit at W6. The following evaluations and sampling are to be performed:

- o Concomitant illness/Concomitant medication
- o Vital signs
- o Adverse events
- Hematology
- o Biochemistry

# 6.2.1.5 Cycle 5 to cycle 16

From cycle 5 (W8) cycles last for 4 weeks and consist of 1 dosing visit only.

Patients who were enrolled according to a previous version of the protocol

will switch to a 4-week cycle schedule of

visits after they have completed and signed an amended informed and consent form. The switch to the new schedule of visits will occur in place of the nearest *odd visit*.

The following pre-dose assessments must be done prior to IPH2201 and ibrutinib administrations:

- Concomitant illness/Concomitant medication
- Tumor assessment:
  - a tumor assessment by physical examination is required at all dosing visits starting from W8 visit (monthly assessments);
  - a CT-scan should be performed at W16 and at any other visit to confirm a CR or progression, whenever one of these events is suspected
- Safety assessments
  - Vital signs (including weight)
  - Physical examination, focused on symptoms and new findings (from screening visit)

[figure not shown]
Release date: Edition number

MOD-3783

12 August 2016

GED version

- ECOG status
- o Adverse events
- o A 12-lead ECG is required at W16 and W32
- Pre-dose Safety laboratory (H0)
  - Hematology
  - Biochemistry, required at W8, W12, W16, then every 2 months, at W24, W32, W40 and W48
  - Coagulation factors to be performed at W8
  - o Urinalysis at W32 only
- Pre-dose PK/PD assessments (H0)
  - o Pharmacokinetics at W12, W20, W28, W36, W44, W52

IPH2201 administration should be performed 28 days +/- 7 days after previous administration.

IP2201 will be administered first, followed by ibrutinib taken after the end of IPH2201 perfusion.

The following post-dose assessments are required:

o PK assessments at H0+1 (end of IPH2201 infusion) at W12, W20, W28, W36, W44, W52

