#### Week 6 day 1 (W6)

The following pre-dose assessments must be done prior to IPH2201 and ibrutinib administrations:

- Concomitant illness / Concomitant medication
- Safety assessments as following:
  - o Vital signs (including weight)
  - Physical examination, focused on symptoms and new findings (from screening visit)
  - o ECOG status
  - Adverse events
- Pre-dose Safety laboratory (H0)
  - o Biochemistry
  - o Hematology
  - o A 12-lead ECG
- Pre-dose PK/PD assessments (H0)
  - o PK
  - 0

IPH2201 administration should be performed 14 days +/- 3 days after the previous administration.

Release date: Edition number 12 August 2016 MOD-3783

GED version

IP2201 will be administered first, followed by ibrutinib, to be taken after the end of IPH2201 perfusion.

- The following post-dose assessments are required at W6 visit:
  - PK assessments at H0+1 (at end of the 1-hour infusion of IPH2201)

### 6.2.2.5 Cycle 5 to cycle 15

From cycle 5 (W8) cycles last for 4 weeks and consist of 1 dosing visit only.

The following pre-dose assessments should be done prior to IPH2201 and ibrutinib administrations:

- Concomitant illness/Concomitant medication
- Tumor assessment:
  - a tumor assessment by physical examination is required at all dosing visits starting from W8 visit (monthly assessments);
  - a CT-scan should be performed at W16 and at any other visit to confirm a CR or progression, whenever one of these events is suspected
- Safety assessments
  - Vital signs (including weight)
  - o Physical examination, focused on symptoms and new findings (from screening visit)
  - o ECOG status
  - Adverse events
  - A 12-lead ECG is required at W16 and W32
- Pre-dose Safety laboratory (H0)
  - Hematology: RBC, WBC with differential count, platelets, hemoglobin; MCV and hematocrit
  - Biochemistry: sodium, potassium, chloride, bicarbonate, calcium, magnesium, phosphate, total proteins, and albumin, urea, uric acid, creatinine, calculated creatinine clearance, ALP, total bilirubin, LDH, AST (SGOT), ALT (SGPT), GGT, amylase, lipase, glucose, CRP and fibrinogen, required at W16, W24, W32, W40 and W48
  - o Urinalysis at predose of W32
- Pre-dose PK/PD assessments (H0)
  - o Pharmacokinetics at W12, W20, W28, W36 and W44

- Testing for IgG, IgM, IgA and total immunoglobulin levels in predose of W16 and W32
- Other specific assessments (H0)

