4.2.2 Main endpoint population

The main endpoint population will include all patients:

Page 14 of 26

TPL N°: eTPL SA-02-01 Of SOP SA-02.08 TPL Effective Date: 31 Mar 2016 TPL Version: 02

Approved in Vault: 3/8/2019

- who have received at least one dose of monalizumab.
- who have received their first dose (W0D1) at least 52 weeks before the data cutoff date.

Patients who discontinued from monalizumab treatment due to disease progression before the end of 8 weeks of treatment will not be part of this population.

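### Protocol 7.2.2 leaves imaging for nodal progression to the investigator, while section 7.2, both flow charts and the later visit sections call for CT, so PFS and DOR events and the week-8 exclusion can rest on different evidence by site

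*Protocol*

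**What the plan says.** **Discretion.** Protocol 7.2.2, in the lymphadenopathy criterion, says CT usually adds little for detecting progression or relapse, and concludes that "the use of imaging methods to follow CLL progression is at the discretion of the investigator".

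**CT on suspicion.**
- Section 7.2, the parent of 7.2.2: "CT scans planned at baseline, week 4, week 16, and whenever a progression or a CR are suspected".
- Phase I flow chart, footnote 14: "New CT-scan should be performed at W4 visit, at W16 visit, at EOS, and to confirm any CR or progression".
- Phase II flow chart, footnote 14: "New CT-scan should be performed at W4, and thereafter at W16 and at EOS, and to confirm any CR or progression".
- Sections 6.2.1.5 and 6.2.2.5 (cycle 5 onward, both phases): "a CT-scan should be performed at W16 and at any other visit to confirm a CR or progression", whenever either event is suspected.
- Sections 6.3 (end of treatment), 6.4 (follow-up) and 6.5 (end of study) carry an equivalent clause.

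**What progression triggers.** Protocol 3.5.1 and 4.3 stop treatment and withdraw the patient, and neither makes a CT a condition. SAP 8.5 counts progression as a PFS and DOR event. SAP 4.2.2 says that patients who stopped monalizumab "due to disease progression before the end of 8 weeks of treatment will not be part of this population". That main endpoint population is the denominator of the CR rate in SAP 8.1. Protocol 4.3.2 and 10.5 replace these patients, yet 10.5 also calls everyone with at least one administration evaluable for efficacy.

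**The concern.** The two sets of text cannot both govern. A site following 7.2.2 may call nodal progression on palpation. A site following section 7.2 or footnote 14 would obtain a CT first. The trial is open-label and single-arm, so neither blinding nor a comparator would absorb a difference in how progression is called.

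Three things depend on that call: PFS and DOR event dates, the end of study treatment and, in the first 8 weeks only, membership of the population in which the primary CR rate is calculated. The last matters most, because it lets an outcome-related judgment decide who is counted for the primary endpoint.

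**Working it through.** **1. Which progression criteria does the conflict touch?** The criteria in 7.2.2, read with the exceptions stated in the plan:

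| Criterion | Usable on treatment? | Can palpation and CT disagree? |
|---|---|---|
| New lesion, or at least 50% growth of a previous site | Yes | Yes; the discretion sentence sits here |
| Liver or spleen enlargement | Yes | Yes |
| Lymphocyte count | Not as sole criterion (3.1.2) | No |
| Cytopenia | No (7.2.2); only after treatment, with marrow biopsy | No |
| Transformation | Yes | No; by lymph node biopsy where possible |

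On treatment, then, most progressions will rest on the first two rows.

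**2. Where does the CT clause apply?** The visit sections for cycles 1 to 4 do not carry it. W4 has a scheduled CT in both phases; W0, W2 and W6 mention none. Cycles 1 to 4 cover the first 8 weeks, the only period in which SAP 4.2.2 can exclude a patient. There the conflict rests on section 7.2 and footnote 14, plus the clause in 6.3 if early discontinuation leads to an end-of-treatment visit.

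**3. How long is the stretch without a scheduled CT?** In phase IIa the end-of-study visit falls 12 months and 1 week after W52: 52 + 52 + 1 = W105. From the W16 scan that is 105 − 16 = 89 weeks. Even the last scan is uncertain: footnote 14 schedules it, whereas 6.5 asks for it only if CR or progression is suspected. This gap bears on PFS and DOR. It does not bear on the CR denominator, because patients who progress after week 8 stay in it.

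**4. The plan's own figures.** Inputs from SAP 3.3.2: n = 27, positive if at least 4 CRs, p0 = 0.05, p1 = 0.20, one-sided alpha 0.05, power 0.80. With X binomial(27, p):
- alpha = P(X ≥ 4 | p = 0.05) = 0.0437
- power = P(X ≥ 4 | p = 0.20) = 0.818

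With n = 26 power is 0.793, so 27 is the smallest sample that meets both targets. The design reproduces.

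**5. What the week-8 exclusion could do.** The documents give no early-progression rate, so 0 to 3 patients is an assumed range.

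(a) Removed from 27 and not replaced, rule of at least 4 kept:

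| Removed | n | Alpha | Power | Estimate with 4 CRs |
|---|---|---|---|---|
| 0 | 27 | 0.0437 | 0.818 | 14.8% |
| 1 | 26 | 0.0387 | 0.793 | 15.4% |
| 2 | 25 | 0.0341 | 0.766 | 16.0% |
| 3 | 24 | 0.0298 | 0.736 | 16.7% |

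(b) Replaced to reach 27, assuming no removed patient could reach CR and a true CR rate of 5% in all treated patients. If a fraction q is removed, the rate among those retained is 0.05/(1 − q):

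| Removed | q | 0.05/(1 − q) | P(at least 4 CRs of 27) |
|---|---|---|---|
| 0 | 0 | 0.0500 | 0.0437 |
| 1 of 28 | 0.0357 | 0.0519 | 0.0489 |
| 2 of 29 | 0.0690 | 0.0537 | 0.0544 |
| 3 of 30 | 0.1000 | 0.0556 | 0.0602 |

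Both tables measure the exclusion and replacement rule. They would be the same if every one of these progressions had been confirmed by CT. The imaging conflict decides only who falls under the rule.

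**The case against.** The strongest reply is that the documents already settle the matter. Section 7.2 sets the trial's CT timing, and a footnote to Appendix III assigns CT to clinical trials and physical examination to general practice. The discretion sentence can be read as concerning routine surveillance, with confirmation left to section 7.2. A W4 scan is scheduled, early discontinuation leads to an end-of-treatment visit with its own CT clause, and the flow charts require a marrow examination at progression.

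Much of this stands as mitigation, but only in part. The end-of-treatment scan can come after treatment has already been stopped. A marrow examination does not establish nodal growth. No text makes CT a condition for calling progression or ranks 7.2 above 7.2.2.

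A reader might also infer more than the documents support:
- *That every visit section asks for a confirmatory CT.* Those for cycles 1 to 4 do not.
- *That any unconfirmed progression removes a patient from the CR denominator.* Only stopping monalizumab for progression before the end of 8 weeks does.
- *That the SAP leaves open whether an unconfirmed progression is an event.* SAP 8.5 asks for no confirmation, while SAP 8.1 and 8.4 ask for it explicitly for CR and for remission with undetectable MRD. The natural reading is that any documented progression counts. What is missing is a standard of evidence, although protocol 7.2.3 speaks of objective progression.
- *That a shift such as 4/28 (14.3%) to 4/27 (14.8%), or the alpha figures above, measures missing CT.* It measures the exclusion rule.
- *That every progression after W16 depends on the imaging rule.* Transformation and post-treatment cytopenia do not.

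**Conclusion.** The contradiction is real and lies in operative endpoint text. Its main consequence is that nodal and organ progressions, which largely determine on-treatment PFS and DOR events, may rest on palpation at one site and CT at another. A narrower consequence is that, in the first 8 weeks, the same undefined judgment can take a patient out of the primary CR denominator, against the evaluability sentence in protocol 10.5.

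The size attributable to the imaging conflict cannot be stated: the documents give neither an early-progression rate nor a rate of progression called without CT. The exclusion rule alone, under the assumptions shown, costs 2 to 8 points of power without replacement (0.818 to 0.793 with one removed, to 0.736 with three). With replacement, it moves the false-positive chance from 0.0437 to between 0.0489 and 0.0602. The assumption that removed patients could not have reached CR may fail for a patient wrongly called progressive, so even the direction for such patients is open. N = 27 and the threshold of 4 CRs are unaffected.

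**What to change.** 1. **Protocol.** The sponsor should reconcile 7.2.2 with section 7.2, footnote 14 of both flow charts, and sections 6.2.1.5, 6.2.2.5, 6.3, 6.4 and 6.5, so that one imaging rule governs, including during cycles 1 to 4. Because progression also ends treatment, which rule applies is for the sponsor to settle.
2. **SAP 8.5.** Flag nodal or organ progressions documented without CT, and repeat PFS and DOR in a sensitivity analysis that handles them separately.
3. **SAP 4.2.2.** State what evidence of progression triggers the week-8 exclusion, and keep patients who do not meet it in the denominator.
4. **SAP 8.1.** Report the CR rate in all treated patients beside the main endpoint population, in line with protocol 10.5.

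The cost is wording changes and a few extra outputs, provided the method of each tumour assessment is recorded in the database; the documents do not show this. The all-treated CR rate may be slightly lower: with 4 CRs and one early progressor replaced, 4/28 = 14.3% beside 4/27 = 14.8%.

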# 7.2.3 Progression free survival (PFS)

PFS is defined as the time from study entry until objective disease progression or death.

# 7.2.4 Overall survival (OS)

OS is defined as the time from study entry until death from any cause, and is measured in the intent-to-treat population.

[figure not shown]

CONFIDENTIAL

Release date: Edition number 12 August 2016

GED version

MOD-3783

[figure not shown]

Release date: Edition number

GED version

# **EXPLORATORY PHARMACOKINETIC / PHARMACODYNAMIC**

[figure not shown]

CONFIDENTIAL

Release date: Edition number

GED version

# 8.10 SPECIAL PROCEDURES

# 8.10.2 Bone Marrow Examination

The following tests will remain exploratory and performed at baseline and whenever a BM examination is indicated during the treatment or the follow-up period.

- 0
- o For BM biopsy, an immunological study of the tissue by immunohistochemistry and quantitative PCR analysis:
  - For tumor cells, the expression of HLA-E and ligands for activating or inhibitory receptors
  - For immune effectors cells, the expression of CD94/NKG2A and other activating or inhibitory receptors

Specimens will be split. One part will be frozen, while the other one will be fixed in formalin and embedded paraffin.

The possibility to assess the function of infiltrated immune effectors extracted from the tumor will be explored if there is enough material.

Release date: Edition number

GED version

# 9 SAFETY ASSESSMENT

The methods for collecting safety data are described below.

# 9.1 ADVERSE EVENT

#### 9.1.1 Definitions

The definitions of Adverse Events (AEs) and Serious Adverse Events (SAEs) are given below. It is the responsibility of the PI to ensure that all staff involved in the study are familiar with the content of this section.

The occurrences of AEs and SAEs are recorded from the time of signed informed consent until the end of the study. All AEs will be graded according to the Common Terminology Criteria for Adverse Events (CTCAE) of the NCI, version 4.03 (June 14, 2010).

# 9.1.1.1 Adverse Event

An AE is any untoward medical occurrence or worsening of pre-existing medical condition in a patient or clinical investigation patient administered an investigational product (study drug), and which does not necessarily have a causal relationship with this treatment. An AE can, therefore, be any unfavorable and unintended sign (including an abnormal laboratory finding), symptom, or disease temporally associated with the use of a medicinal product, whether or not related to the medicinal product.

An AE related to the IMP is defined as an Adverse Reaction (AR) and includes all unintended responses to an investigational product related to any dose (see section 9.1.1.4). Symptoms and lab abnormalities not related to the IMP should not be reported as AEs but every effort has to be made to establish a cause and a diagnosis which has to be then reported as AE. In addition any procedure (e.g. surgery, stent, etc.) should not be reported as AE but the event which led to the procedure (e.g. appendicitis, myocardial infarction, etc.).

Disease (CLL) relapse/progression is not considered as an Adverse Event in this study.

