# 9.1.2 Adverse Events Collection and Reporting

All AEs and SAEs, whether related or not related to study drug, including those thought to be associated with protocol-specified procedures, must be collected throughout the study from the time of patient signing the consent form until the end of study visit, or until the patient's last study visit. All reported AEs and SAEs will be followed until resolution. The Investigator should take appropriate measures to follow all AEs until clinical recovery is complete and laboratory results have returned to normal, or until progression has been stabilized, or until death, in order to ensure the safety of the patients. This may imply that observations will continue beyond the last planned visit per protocol, and that additional investigations may be requested by the monitoring team up to as noticed by the Sponsor. When treatment is prematurely discontinued, the patient's observations will continue until the end of the study as defined by the protocol for that patient.

All AEs will be recorded on the eCRFs. The records will describe the nature (diagnosis or single syndrome as much as possible, alternatively signs and symptoms) severity, using the NCI CTCAE term (version 4.3 of June 14, 2010), date/time of onset, date/time of end, actions taken with respect to IMP, corrective treatment/therapy given, additional investigations performed, outcome, and causality (relationship to study treatment according to the investigator's assessment).

It will be specified whether the event is serious or not according to the definition of SAE (See section 9.1.1).

A sponsor safety representative will determine the causal relationship when it is not clearly provided by the investigator.

Laboratory, vital signs or ECG abnormalities are to be recorded as AEs only if:

- o Symptomatic and/or
- Requiring either corrective treatment or consultation, and/or
- Leading to IMP discontinuation or modification of dosing, and/or
- Fulfilling a seriousness criterion

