#### 9.1.4 Abnormal laboratory values/vital signs

The reporting of laboratory / vital signs / ECG abnormalities as laboratory findings / vital signs / ECG and as AEs should be avoided. They should not be reported as AEs (using the NCI CTCAE version 4.3 of June 14, 2010 terminology) unless any one of the following are met:

- o Any criterion for a SAE is fulfilled
- The laboratory / vital signs / ECG abnormality causes the subject to discontinue from the study treatment

Release date: Edition number

MOD-3783

12 August 2016

GED version

- The laboratory / vital signs / ECG abnormality causes the subject to interrupt the study treatment
- The laboratory / vital signs / ECG abnormality requires intervention as corrective treatment or consultation and/or
- Symptomatic and/or
- o The Investigator believes that the abnormality should be reported as an AE

All laboratory tests for which abnormal results are collected after the initiation of study treatment should be repeated until the values return to normal or to a stable status. Abnormal results are defined as those falling out of the normal laboratory range and that are clinically significant. The frequency with which such checks should be made will be defined by the investigator's opinion depending on the degree of abnormality.

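### Protocol 9.1.1.1 bars AE entries for undiagnosed, non-serious symptoms and qualifying laboratory abnormalities judged unrelated to IPH2201, in conflict with its own AE definition and with 9.1.2 and 9.1.4

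*Protocol*

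**What the plan says.** Protocol 9.1.1.1 defines an AE as any unfavourable sign, abnormal laboratory finding or symptom, "whether or not related to the medicinal product". The next paragraph then says: "Symptoms and lab abnormalities not related to the IMP should not be reported as AEs", and continues "but every effort has to be made to establish a cause and a diagnosis which has to be then reported as AE". Procedures are handled in the same spirit: the event that led to the procedure is the AE.

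Protocol 9.1.2 gives the collection rule: "All AEs and SAEs, whether related or not related to study drug, including those thought to be associated with protocol-specified procedures, must be collected". It describes the nature of the entry as "diagnosis or single syndrome as much as possible, alternatively signs and symptoms". It adds: "Laboratory, vital signs or ECG abnormalities are to be recorded as AEs only if" at least one of four conditions is met. These are symptoms, a need for treatment or consultation, IMP discontinuation or a dosing change, and seriousness. Section 9.1.4 has a similar list and adds a further route: "The Investigator believes that the abnormality should be reported as an AE". Neither list mentions relatedness. Sections 9.1.3 and 9.1.3.1 require SAEs to be reported regardless of causality.

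Four other places matter:
- Section 5.1 identifies the IMP as IPH2201, and ibrutinib has its own section, 5.2.
- Section 5.1.1 says the study is open label, and 9.1.1.4 has the investigator judge relatedness.
- Section 3.1.1 makes AE occurrence part of the phase Ib primary endpoint, and 3.1.2 makes safety a phase IIa secondary endpoint.
- SAP 9.3 tabulates all treatment-emergent AEs, and separately those related to monalizumab (IPH2201) and those related to ibrutinib.

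**The concern.** Two parts of the protocol give a site opposite instructions for the same event. Take a non-serious symptom that the investigator thinks is unrelated to IPH2201 and for which no diagnosis emerges. Section 9.1.2 has it recorded; 9.1.1.1 does not. A site that follows 9.1.1.1 uses the causality judgement to decide whether an AE exists, when it should only be an attribute of a recorded AE.

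The meaning of IMP adds to this. Read literally, a symptom attributed only to ibrutinib is unrelated to the IMP and falls under the bar. Protocol 1.1.5.1 describes ibrutinib's commonest adverse events as fatigue, constitutional complaints and unspecific digestive trouble of mild to moderate severity. Events of that kind are often non-serious and may never receive a diagnosis, yet the SAP plans tables of ibrutinib-related events.

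The filter works in one direction: it can remove AE entries but not add them. SAP 9.3 counts an AE with a missing relationship as related, but that cautious rule acts only on events that were entered.

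**Working it through.** The plan states no figure on this point, so there is nothing to reproduce. The check sets the rules side by side for an event judged unrelated to IPH2201.

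| Event | 9.1.1.1, read literally | 9.1.2 and 9.1.4 | Conflict |
|---|---|---|---|
| Serious | Reported under the SAE rule (9.1.3, 9.1.3.1) | Reported | No |
| Non-serious, diagnosis established | Diagnosis reported | Diagnosis reported | No |
| Non-serious symptom, no diagnosis | Not reported | Sign or symptom recorded | Yes |
| Non-serious laboratory abnormality meeting a listed criterion, no diagnosis | Not reported | Recorded | Yes |
| Laboratory abnormality meeting no criterion | Not reported | Not recorded | No |
| Non-serious symptom attributed only to ibrutinib, no diagnosis | Not reported | Sign or symptom recorded | Yes |

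The exposure is therefore confined to rows three, four and six. In row two no patient is lost, although the coded term is the diagnosis and not the symptom.

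**Illustration of scale, on assumed values only.** Let p be the true incidence of an event, and u the share of its cases that are judged unrelated to IPH2201, remain undiagnosed, and occur at sites following 9.1.1.1. Then

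reported incidence = p × (1 − u).

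With 27 patients, the planned number for phase IIa efficacy (SAP 3.3.2):

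| p | u | Reported incidence | Expected patients |
|---|---|---|---|
| 20% | 0 | 20% | 27 × 0.20 = 5.4 |
| 20% | 10% | 18% | 5.4 × 0.9 = 4.9 |
| 20% | 30% | 14% | 5.4 × 0.7 = 3.8 |
| 20% | 50% | 10% | 5.4 × 0.5 = 2.7 |
| 40% | 0 | 40% | 27 × 0.40 = 10.8 |
| 40% | 10% | 36% | 10.8 × 0.9 = 9.7 |
| 40% | 30% | 28% | 10.8 × 0.7 = 7.6 |
| 40% | 50% | 20% | 10.8 × 0.5 = 5.4 |

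The documents give neither p nor u. If a diagnosis is always found, or every site follows 9.1.2, u is 0 and nothing is lost.

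**The case against.** The best defence is that 9.1.1.1 intends only that sites code the diagnosis and not its components. The second half of the sentence supports this, as does the parallel rule for procedures. Section 9.1.1.1 is also a definition, while 9.1.2 is the operative collection section, and a site following 9.1.2 would record the symptom. The scale in 9.1.1.4 has categories for unrelated AEs, so the protocol expects such entries. It also narrows the gap: the unrelated category presupposes an extraneous cause, which is hard to name when no cause was found, and an event whose link cannot be excluded is classed as possibly related.

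Much of this stands. It limits the exposed class and makes loss conditional on which section a site follows. It does not remove the conflict. The sentence has no fallback for an undiagnosed event, the probably-not-related category leaves room for such events, and the restriction applies only to events judged unrelated. If diagnosis coding were the sole intent, attribution would play no part.

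Three stronger readings are tempting, and the documents do not support them:
- **AE incidence in general depends on attribution.** It does not: SAEs and diagnosed events are reported either way.
- **Undiagnosed unrelated symptoms are never recorded.** Section 9.1.2 says they should be.
- **Dose escalation is compromised.** The DLT criteria in 9.3 rest on grade, blood counts, bleeding and dose delay, with no relatedness condition, and the documents do not show that DLTs would be missed. It is true only that the safety committee, which analyses causality in phase Ib, could not re-judge an event that was never entered.

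**Conclusion.** The internal inconsistency is real and should be corrected, with limited reach. It concerns non-serious symptoms and qualifying laboratory abnormalities that stay undiagnosed and are judged unrelated to IPH2201, including, on a literal reading, those attributed to ibrutinib alone. For this class, whether an AE is counted depends on which section the site follows and, under 9.1.1.1, on an open-label judgement.

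The direction is known: any loss lowers counts in the phase Ib primary safety endpoint, the phase IIa safety endpoint and the SAP's treatment-emergent AE tables. The size is not known. As the trial is single-arm, the issue is under-counting, not a distorted comparison between arms. The conclusion assumes that some sites apply 9.1.1.1 as written and that some such events remain undiagnosed.

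**What to change.** Replace the whole sentence in Protocol 9.1.1.1 with:

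> Report the diagnosis as the AE when one is established; otherwise record the sign or symptom as the AE whatever its attribution to IPH2201 or ibrutinib. Laboratory, vital sign and ECG abnormalities are recorded as AEs according to the criteria in 9.1.2 and 9.1.4, whatever the attribution. Relatedness is recorded as a separate field.

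It is not enough to delete the qualifier about the IMP. What remained would bar all symptoms and laboratory abnormalities, a wider prohibition than the present one. The replacement also has to keep the laboratory criteria, so that minor laboratory findings do not become AEs.

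The protocol plans the last patient visit for the first quarter of 2019 and the SAP carries a 2019 approval date, so data may already have been collected under the current wording. In that case the study report should state which rule the sites followed.

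The cost is one replaced passage and slightly more AE entries.
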